### **7.2 PARTICIPANT DISCONTINUATION/WITHDRAWAL FROM THE STUDY**

#### **7.2.1 Patient Discontinuation and Stopping Rules**

The Investigator in conjunction with the Sponsor may also, at their discretion, discontinue the patient from participation in the study at any time if discontinuation would be in the patient's best interest. If a patient meets any of the criteria listed below, the patient should complete the assessments for the ET Visit (see [Table 2](#) and [Table 3](#)).

Reasons for discontinuing a patient may include, but are not necessarily limited to, the following:

- Severe and life-threatening pemphigus disease activity
- Grade 4 rilzabrutinib-related TEAE
- Serious allergic reaction to rilzabrutinib or placebo including anaphylactic reaction
- A patient in the Blinded Treatment Period requiring an additional “top up” dose of rituximab after their initial rituximab course of treatment or a patient in the Open-Label Extension Period or Long Term Extension Period requiring rituximab
- Human immunodeficiency virus (HIV)/acquired immune deficiency syndrome (AIDS), viral hepatitis (B and C) infection occurring during the study
- Pregnancy
- Any medical condition or personal circumstance that, in the opinion of the Investigator, exposes the patient to risk if the patient continues with rilzabrutinib or placebo or that prevents the patient’s adherence to the protocol
- If in the Investigator’s or the Sponsor’s judgment, discontinuation is in the patient’s best interest
- Violation of protocol inclusion or exclusion criteria, if, in the opinion of the Investigator and the Sponsor, the violation would significantly compromise data interpretation
- Discontinuation of the study by the Sponsor.

For participants in Germany, please see specific instructions in Appendix 10 [Section 12.10](#).

No follow-up or additional procedures will be performed on patients who discontinue before receiving rilzabrutinib or placebo. For patients who discontinue after receiving any amount of rilzabrutinib or placebo, the reason for a patient’s discontinuation from the study must be clearly documented in the patient’s medical records and on the appropriate page of the eCRF, and patients will be asked to complete the ET assessments (see [Table 2](#) and [Table 3](#)).

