#### **Primary:**

The proportion of patients who are in CR from Week 29 (Visit) to Week 37 (Visit) with a CS dose of  $\leq 10$  mg/day.

- A Cochran-Mantel-Haenszel (CMH) general association test stratified by disease type (PV or PF) and disease history (newly diagnosed or relapsing) will be used to compare rilzabrutinib with placebo. Newly diagnosed pemphigus is defined as patients diagnosed  $\leq 6$  months prior to Screening. Relapsing, chronic pemphigus is defined as patients diagnosed  $> 6$  months prior to Screening.

Patients who drop out of the trial, withdraw, or who receive a rituximab dose prior to Week 37 will count as non-responders in the analysis.

The primary efficacy analysis will be performed using a CMH general association test stratified by disease history (newly diagnosed or relapsing) to compare rilzabrutinib with placebo.

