### **2.3.2.3. Other Secondary Endpoint(s)**

The other secondary efficacy endpoints of this study include the following:

- The proportion of patients who are in CR from Week 29 to Week 37 with a CS dose of  $\leq 5$  mg/day
- The proportion of patients who have a PDAI score  $< 3$  from Week 29 to Week 37 with a CS dose  $\leq 10$  mg/day
- Cumulative duration of CR with a CS dose  $\leq 10$  mg/day from Baseline to Week 61, and from baseline to Week 109
- Cumulative duration of CR with a CS dose = 0 mg/day from Baseline to Week 61, and from baseline to Week 109
- Glucocorticoid Toxicity Index (GTI) score at Week 37
- Change in PDAI score from baseline to Weeks 5, 13, 25, 37, 61 and 109
- Change in Autoimmune Bullous Disease Quality of Life (ABQOL) score from baseline to Weeks 5, 13, 25, 37, 61, and 109
- Proportion of patients with ABQOL Score of zero at Weeks 5, 13, 25, 37, 61, and 109
- Change in EuroQOL-5 Dimension 5 Level (EQ-5D-5L) results (visual analog scale [VAS] results and individual dimension) scores from Baseline to Weeks 5, 13, 25, 37, 61, and 109
- Time to first CR with a CS dose  $\leq 10$ mg/day from Baseline to Week 61, and from Baseline to Week 109
- Total number of disease flares/relapses from initial CDA to Week 37
- Time to initial flare/relapse from initial CDA to Week 37
- Proportion of patients with 3 or more lesions within 1 month that do not heal spontaneously within 1 week, or by the extension of established lesions, from Baseline to Week 37.
- Proportion of patients with at least one disease flare/relapse from initial control of disease activity (CDA) to Week 37.

- Cumulative duration of CR with a CS dose  $\leq$  10 mg/day, from Week 37 to Week 61.
- Cumulative duration of CR with a CS dose = 0 mg/day, from Week 37 to Week 61

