#### 6.1.5.1. Imputation Procedures for the Primary Efficacy Endpoint

For the primary efficacy endpoint (the proportion of patients who are in CR from Week 29 to Week 37 with a prednisone dose of  $\leq 10$  mg/day), patients with missing data due to study withdrawal will be considered as non-responders. A patient who received a rituximab dose prior to Week 37 will also be counted as a non-responder. [REDACTED]

[REDACTED]

- [REDACTED]
- [REDACTED]

[REDACTED]

[REDACTED]

[REDACTED]

[figure not shown]
[REDACTED]

[REDACTED]

Tipping point analyses (Yan, 2009) will be done to investigate the impact of missing data and lost to follow-up (LTF). The tipping point analysis will look at all possible combination of

converting missing data to a responder, starting at 0 and ending at all are responders. The cases where the statistical significance tips from significance to non-significance (defined as a two sided p-value  $>0.05$ ) will be listed. A complete list of all combinations will also be presented. If the imbalances that leads to a change in interpretation are clinically implausible then the results of the primary analysis will be deemed reliable

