**Other responder analysis:**

- Proportion of patients with ABQOL Score of zero at Weeks 5, 13, 25, 37, and 61 the patient will be counted as a non-responder starting from the date of first dose of rituximab for the responder analysis.

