**Table 4: Event and Censoring Details for Time to First CR with a CS dose at or below 10 mg/day**

Situation	Date of First CR/ Date of Censoring	Censored/ Event
No post baseline assessments	Date of first dose	Censored
Patient in CR status and with a CS dose of $\leq 10$ mg/day	First date that patient is in CR status and with a CS dose of $\leq 10$ mg/day as identified in Section 6.1.9.	Event
Rituximab administered	Date of first Rituximab administration	Censored
No CR with a CS dose of $\leq 10$ mg/day during the Blinded Treatment Period	Date of last efficacy assessment during blinded treatment phase (through Week 37)	Censored
Study discontinuation	Date of last efficacy assessment prior to or on the date of treatment discontinuation	Censored
Death before CR	Date of death	Censored

Note: Patients will be censored prior to a CR event at the earliest date of the censored events above should a censoring reason occur. Censoring reasons may be categorized for reporting (eg, by discontinuation reason).

- Three or more lesions within 1 month that do not heal spontaneously within 1 week or extension of established lesions = Yes if any of the following conditions are satisfied:
  - eCRF entry “Have new lesions appeared within a month that did not heal spontaneously within 1 week? OR Have there been extension of established lesions?” = Yes for any visits from Baseline up to Week 37.
  - At this visit, Has a Relapse occurred or is continuing?

The number of instances with investigator assessments of disease worsening will also be derived and categorized for reporting as 0, 1, 2, and  $\geq 3$ . After the first worsening, a patient can have additional worsening, but only after the patient returns to CDA first, and then the next worsening can happen.

- PDAI score  $< 3$  from Week 29 to Week 37 with a CS dose of  $\leq 10$  mg/day = Yes if the following conditions are both satisfied:
  - PDAI  $< 3$  = Yes for all visits from Week 29 through Week 37
  - Daily prednisone dose is  $\leq 10$  mg/day from Week 29 through Week 37 as defined in Section 6.1.9.
  - No Rituximab therapy prior to Week 37.

After applying the CS dose imputation as described in Section 6.1.5.2, a patient with partial missing data (missing PDAI assessment or CS dose) or complete missing data at any scheduled visit will be considered as a non-responder.

- Change from baseline = value at current time point – value at Baseline.

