- PDAI Total Score = the Total PDAI activity score as reported on the PDAI Total Score CRF (possible range of 0 to 250) as the sum of the individual skin activity, scalp activity and mucosal activity scores, higher score corresponding to worsening.
- PDAI activity subscores for skin (range 0 to 120), scalp (range from 0 to 10) and mucosal (range from 0 to 120)
- ABQOL Score of zero, = Yes if zero; = No if ABQOL is present and nonzero; missing otherwise.
- TABQOL = Sum of the 17 items of the ABQOL Questionnaire. Each item is scored on a scale of 0-3 for each of the 4 options (all the time, sometimes, occasionally and never), with 0 being the least severe and 3 being the most severe. No imputation will be done for missing item, therefore the total score will be missing if any item is missing.
- EQ-5D-5L: The EQ-5D-5L comprises the EQ-5D 5 dimensions (mobility, self-care, usual activities, pain/discomfort and anxiety/depression) and a visual analogue scale (VAS).

Each dimension has 5 levels: no problems, slight problems, moderate problems, severe problems and extreme problems. Overall health state is then defined as a 5-digit number. The health utility index value will be calculated using the crosswalk value sets provided in the EQ-5D-5L Index Value Calculator created by the EuroQol Group and using mapping function developed by Van Hout et al.. The values sets based on UK population will be used for all countries. The health utility score will be missing if response to one or more dimension is missing.

- The EQ VAS records the respondent’s self-rated health on a 20 cm vertical VAS with endpoints labelled 0 (‘the worst health you can imagine’) to 100 (‘the best health you can imagine’). This information can be used as a quantitative measure of health as judged by the individual respondents. EQ VAS will be described as given by patient. Missing data will not be imputed.
- At least one relapse/flare after initial CDA to Week 37 = Yes if the following condition is satisfied:
  - eCRF entry “At this visit, Has a Relapse occurred or is continuing?” = Yes for any visits from CDA to Week 37.
  - If a patient received a rituximab dose prior to Week 37, the patient will be counted as Yes.

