	Cumulative duration of CR with a CS dose = 0 mg/day (days) from Baseline to Week 61	Zero-inflated negative binomial with terms for treatment group and disease history with an offset term based on the number of days on study during the Open-Label Extension Period
	GTI scores at Week 37	Analysis of covariance, with treatment, disease history as fixed effects, and baseline GTI score, baseline CS dose as covariates
	Change from Baseline in PDAI Score at Weeks 5, 13, 25, 37, and 61	MMRM with terms for treatment, week, baseline score, disease history, and treatment by week interaction
	Change from Baseline in ABQOL Score at Weeks 5, 13, 25, 37, and 61	MMRM with terms for treatment, week, baseline score, disease history, and treatment by week interaction
	Proportion of patients with ABQOL Score of zero at Weeks 5, 13, 25, 37, and 61	Cochran-Mantel-Haenszel test stratified by disease history at each visit
	Change from Baseline in EQ-5D-5L visual analog scale [VAS] results and individual dimension score categories at Weeks 5, 13, 25, 37 and 61	Continuous outcomes: MMRM with terms for treatment, week, baseline score, disease history, and treatment by week interaction. Categorical outcomes: Cochran-Mantel-Haenszel test stratified by disease history

	Endpoint	Analysis Method
	Time to first flare/relapse from initial CDA to Week 37	Log rank test stratified by disease history
	Time to first CR with a CS dose $\leq$ 10mg/day, from Baseline to Week 61	Log rank test stratified by disease history
	Proportion of patients with 3 or more lesions within 1 month or extension of established lesions that do not heal spontaneously within 1 week from Baseline to Week 37	Cochran-Mantel-Haenszel test stratified by disease history
	Total number of disease flares/relapses from initial CDA to Week 37	Zero-inflated negative binomial with terms for treatment group and disease history with an offset term based on the number of days on Post initial CDA

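### Patients who withdraw without rituximab drop out of the ABQOL-zero comparison at later visits, whereas the primary and PDAI<3 analyses count them as failures

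*SAP*

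**What the plan says.** The endpoint is listed in SAP 2.3.2.3 as "Proportion of patients with ABQOL Score of zero at Weeks 5, 13, 25, 37, 61, and 109". SAP Table 6 gives the test, for visits up to Week 61, as "Cochran-Mantel-Haenszel test stratified by disease history at each visit", and SAP Section 8 places all efficacy analyses on the mITT population.

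The responder status is defined in SAP 6.1.8: "ABQOL Score of zero, = Yes if zero; = No if ABQOL is present and nonzero; missing otherwise". The only further rule shown for this endpoint is in SAP 6.1.5.2 and concerns rescue: "the patient will be counted as a non-responder starting from the date of first dose of rituximab for the responder analysis".

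Other responder endpoints are handled differently. For the primary, SAP 6.1.5.1 says "patients with missing data due to study withdrawal will be considered as non-responders", and Protocol 9.3.5 says "Patients who drop out of the trial, withdraw, or who receive a rituximab dose prior to Week 37 will count as non-responders in the analysis". For the PDAI<3 responder, SAP 6.1.8 says that partial or "complete missing data at any scheduled visit will be considered as a non-responder". For the relapse and worsening proportions, SAP 6.1.5.2 counts a missing value as an event, with one narrow exception.

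SAP 6.1.5 states in general that patients who withdraw or miss a visit will have missing primary and secondary efficacy data imputed by the criteria in that section. The visible text contains no such criterion for ABQOL-zero.

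**The concern.** A withdrawn patient completes no later questionnaires. Under the stated derivation that patient is neither a success nor a failure but missing, and a CMH test on the derived variable leaves the patient out. The comparison then covers patients with a score in the window plus rescued patients, not everyone in the mITT population.

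Some of this missingness is tied to outcome by the protocol itself. Protocol 7.2.1 lists "Severe and life-threatening pemphigus disease activity" among the reasons for discontinuing a patient. Protocol 6.5.1 has patients who need another immunosuppressant withdrawn. Appendix 1 has study drug stopped for a life-threatening flare, and its definition of a qualifying relapse says such a patient should be withdrawn. So, within one endpoint, a patient rescued with rituximab for a less severe relapse counts as a failure, while a patient withdrawn for a worse flare without rituximab disappears.

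What is at stake is a reported difference and nominal p-value for a patient-reported benefit, which could move with the pattern of withdrawal in the two arms.

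**Working it through.** The documents give no expected ABQOL-zero rate, withdrawal rate or power for this endpoint, so there is no figure of the plan's own to reproduce. The check has two parts.

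**1. Tracing patients through the rules**

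- *Rituximab in Week 20 for a second qualifying relapse.* SAP 6.1.5.2 makes this patient 'No' at Weeks 25 and 37, even if the patient later leaves.
- *Withdrawn in Week 20 for a life-threatening flare, no rituximab.* There is no score at Weeks 25 and 37, so SAP 6.1.8 gives missing at both. An early-termination ABQOL could fill a visit if it fell in that visit's window (SAP 6.1.6). Week 20 begins on Day 134, which lies in the Week 21 window (Days 127–154), and Week 21 is not an ABQOL visit.
- *Still on study, one questionnaire missed.* Also missing at that visit.

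Two other provisions do not close the gap. The version 2 entry in SAP Table 1 that extends imputation to other secondary endpoints is limited to CS and CR status. The sentence in SAP 6.1.8 that bases derived variables on imputed data is limited to primary or key analyses. The tipping point analyses cover only the primary.

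**2. Illustrating the size**

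The rates below are assumptions. Let *r* be an arm's rate with unrescued withdrawals counted as failures, and *d* the share of the arm lost without rituximab and without a score in the window. The lost patients add nothing to the numerator and are removed from the denominator, so

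observed-case rate = *r* / (1 − *d*).

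With *r* = 30% active and 15% placebo (difference 15 points):

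- *d* = 20% v 10%: 30/0.80 = 37.5%; 15/0.90 = 16.7%; difference 20.8 points.
- *d* = 10% v 20%: 30/0.90 = 33.3%; 15/0.80 = 18.75%; difference 14.6 points.

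At about 60 per arm (Protocol 4.1), a loss of 10% to 20% is 6 to 12 patients per arm.

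The calculation can also run the other way, fixing the rate *q* among observed patients at 30% v 15%, so that the failure-inclusive rate is *q*(1 − *d*):

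- *d* = 10% v 10%: 27.0% − 13.5% = 13.5 points. Power is 46% observed-case (54 v 54) and 45% with withdrawals as failures (60 v 60), by the two-proportion normal approximation, unstratified, two-sided 0.05.
- *d* = 25% v 10%: 22.5% − 13.5% = 9.0 points.
- *d* = 10% v 25%: 27.0% − 11.25% = 15.75 points.

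Either way, equal losses change the test little, and unequal losses change the estimate in a direction set by which arm loses more patients.

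**The case against.** Several objections have force.

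*Counting withdrawal as failure is not neutral.* Listed discontinuation reasons include pregnancy, new HIV or hepatitis infection and sponsor discontinuation and, in Germany, a positive SARS-CoV-2 test. None of these shows a failure of quality of life. This stands, and is the reason to keep an observed-case analysis alongside.

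*The plan is not uniform elsewhere.* EQ VAS is not imputed, and the derived variable for remission on zero CS at Week 61 is missing when data are incomplete, unless remission is documented on both sides of the gap. This stands in part. EQ VAS goes into a repeated-measures model that uses a patient's earlier scores, and the Week 53 to 61 zero-CS endpoint carries no randomised comparison. Neither applies to a per-visit CMH test.

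*Text may be out of sight.* SAP 6.1.5.1 is partly redacted, and SAP 6.1.8 refers to a CS imputation in 6.1.5.2 that is not visible. A hidden ABQOL rule cannot be excluded, but it would contradict the explicit derivation in 6.1.8.

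A reader might also infer three stronger things that the documents do not support:

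- *That patients discontinued for a 'top up' rituximab dose are lost.* They have already had rituximab, so they stay in as failures.
- *That each arm's rate is inflated by 1/(1 − d), with d its whole withdrawal rate.* Withdrawals after rescue remain in the denominator, and an early-termination score may fill a window. Only unrescued patients without a score count towards *d*.
- *That the test has an inflated type I error.* With 60 per arm, equal failure-inclusive rates of 30% and withdrawal of 25% v 10%, the observed-case test rejects about 10% of the time. That null presupposes that withdrawal is failure. Under equal observed rates of 30% and the same withdrawal, the failure rule gives 22.5% v 27.0% and itself rejects about 9% of the time. Neither figure is a property of the plan.

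**Conclusion.** The point holds as a minor one. As the SAP reads, a patient who withdraws without rituximab and has no ABQOL score in the window leaves the ABQOL-zero comparison at later visits. This conflicts with the imputation promised in SAP 6.1.5, and it differs from the failure handling of the primary and the PDAI<3 responder. It also treats a rescued relapse as failure while dropping an unrescued, possibly worse one.

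Neither the size nor the direction of the effect can be stated. The illustrated 20.8 or 14.6 points in place of 15 rests on assumed rates of 30% v 15% and unrescued withdrawal of 20% v 10% or the reverse. The documents do not show that either arm would be favoured.

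The consequence is limited. SAP 6.1.4 treats endpoints outside the hierarchy as exploratory, and Protocol 9.3.6 has the other secondary endpoints analysed mainly descriptively. No formal claim or family-wise error rate depends on this one.

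**What to change.** In SAP 6.1.8 and 6.1.5.2, score ABQOL-zero as 'No' at each scheduled visit after study withdrawal when no ABQOL score falls in the analysis window, in addition to the existing rituximab rule. This also reconciles 6.1.8 with the general statement in 6.1.5.

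If an isolated missed visit in a patient still on study is to be inferred from zero scores at both adjacent ABQOL visits, exclude Week 37. The next ABQOL is at Week 39, when every patient is on open-label drug, and SAP 6.1.5.2 already bars this inference at Week 37 for the relapse and worsening proportions.

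Keep the observed-case result as a sensitivity analysis.

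The cost is SAP wording and programming. Reported rates will be slightly lower, and some withdrawals unrelated to disease will count as failures; the observed-case analysis lets the reader judge how much that matters.

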#### **8.4.10 Autoimmune bullous disease quality of life (ABQOL)**

The Autoimmune Bullous Disease Quality of Life (ABQOL) questionnaire was developed in Australia as a patient-based measure to determine quality of life in patients with autoimmune bullous disease (Appendix 3 [Section 12.3](#)). The ABQOL was found to be more sensitive than both the 36-Item Short Form Health Survey ( $p = 0.01$ ) and the Dermatology Life Quality Index ( $p = 0.02$ ). It was also found to be a reliable instrument evaluated by internal consistency with a Cronbach  $\alpha$  coefficient of 0.84 (13).

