#### **8.4.11 Treatment autoimmune bullous disease quality of life (TABQOL)**

The TABQOL questionnaire is a patient-based tool that measures the subjective element of disease progression and burden attributable to the side effects of autoimmune bullous disease (AIBD) treatment, with higher scores indicating worse quality of life (QOL) (14). Refer to Appendix 4 [Section 12.4](#) for the scale.

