### 2.3.4. Exploratory Endpoints

Exploratory endpoints and analyses include the following:

- Exploratory PK/PD analysis will examine the effects, if any, of covariates on PK and/or PD, and the relationship between PK, PD and efficacy in this population
- Number and type of hospitalizations, outpatient medical visits, concomitant medication use, adverse events and other relevant outcomes
- Change from baseline in PDAI by visit and the temporal relationship to changes in quality of life and health economic variables
- Proportion of patients with relapse after achievement of CR between Baseline and Week 61, and between Baseline and Week 109
- Proportion of patients initially randomized to PRN1008 that are in CR with a zero CS dose, from Week 53 to Week 61 (no randomized treatment comparison)
- Proportion of patients initially randomized to placebo that are in CR with a zero CS dose, from Week 53 to Week 61 (no randomized treatment comparison)
- Change in Treatment of Autoimmune Bullous Disease Quality of Life (TABQOL) score from Baseline to Weeks 5, 13, 25, 37, 61, and 109
- Total number of disease flares/relapses from Week 37 to Week 61, and from Week 61 to Week 109
- (Optional) Blood samples for exploratory analysis of vaccine IgG response during treatment.

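### SAP 6.1.8 names the ABQOL questionnaire as the item source for the TABQOL score, a drafting error confined to an exploratory endpoint

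*SAP*

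**What the plan says.** The only TABQOL scoring rule in the visible SAP is one bullet in Section 6.1.8. It has three parts:

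- source and item count: "TABQOL = Sum of the 17 items of the ABQOL Questionnaire";
- coding: "Each item is scored on a scale of 0-3 for each of the 4 options", with 0 the least severe and 3 the most severe;
- missing items: "No imputation will be done for missing item, therefore the total score will be missing if any item is missing". This sentence carries the citation to SAP reference 10, the development and validation study of the TABQOL questionnaire.

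The exploratory endpoint that depends on this rule, in SAP 2.3.4, is "Change in Treatment of Autoimmune Bullous Disease Quality of Life (TABQOL) score from Baseline to Weeks 5, 13, 25, 37, 61, and 109".

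The protocol keeps the two instruments apart. Section 8.4.10 calls ABQOL "a patient-based measure to determine quality of life in patients with autoimmune bullous disease". Section 8.4.11 says TABQOL captures disease progression together with "burden attributable to the side effects of autoimmune bullous disease (AIBD) treatment, with higher scores indicating worse quality of life". Each has its own appendix (3 for ABQOL, 4 for TABQOL), and Appendix 9A lists them as two questionnaires to be sent to patients at remote visits.

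For ABQOL, Section 6.1.8 defines only a flag: "ABQOL Score of zero, = Yes if zero; = No if ABQOL is present and nonzero; missing otherwise".

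**The concern.** Section 6.1.8 is where a programmer looks for score definitions, and the protocol synopsis makes the SAP the final authority on analysis. The rule given there names the wrong questionnaire. If it were followed to the letter, tables headed TABQOL would contain answers to the ABQOL form. A change in the burden of the disease could then be read as a change in the burden of its treatment, and the TABQOL answers collected from patients would not be scored at all.

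A related gap concerns ABQOL. Two other secondary endpoints (change from baseline, and the proportion with a score of zero) rest on an ABQOL total. The visible SAP gives no formula or missing-item rule for that total.

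**Working it through.** No sample size, power or alpha figure is involved, and the plan states no figure to reproduce. The check is a comparison of the texts, with one line of arithmetic.

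**1. Which instrument does the bullet mean?**

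| Element | Points to |
|---|---|
| Label of the bullet (SAP 6.1.8) | TABQOL |
| Cited source (SAP reference 10) | TABQOL |
| Endpoint served (SAP 2.3.4) | TABQOL |
| Questionnaire named as item source (SAP 6.1.8) | ABQOL |

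Three of the four elements agree; the named source is the odd one out.

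**2. Could the two names denote one instrument?** No. Protocol 8.4.10 and 8.4.11, Appendices 3 and 4, and the remote-visit list in Appendix 9A all treat them as two.

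**3. Is the line corrected elsewhere?** The change history (SAP 2.2) records that the TABQOL analysis moved to the exploratory section but says nothing about scoring. Table 6 has no TABQOL row. Section 8.4 describes the summaries but not the score. So the bullet stands alone.

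**4. What does the rule imply numerically?** With 17 items scored 0 to 3, the total runs from 0 to 17 × 3 = 51. The SAP states no range. The questionnaire pages are not visible in the documents available for this review, so neither the 17-item count nor the response options can be checked for either instrument. The severity direction (3 worst) does agree with Protocol 8.4.11, where higher scores are worse.

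**5. What analysis does it feed?** SAP 8.4 gives observed values and changes from baseline by visit as summary statistics. Under SAP 6.1.4 only the primary and key secondary endpoints are in the testing sequence. Protocol 9.3.8 plans a mixed model for TABQOL, which SAP 8.4 does not carry over. That is a separate discrepancy, and the endpoint is exploratory in both documents.

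**6. What about ABQOL?** Change in ABQOL is analysed by mixed model, and ABQOL zero by a stratified Cochran-Mantel-Haenszel test (SAP Table 6 and 8.3). The zero flag presupposes a total. Take a form with one blank item and every answered item at 0. If any blank item makes the total missing, the flag is missing. If blanks are tolerated, the flag is Yes. The SAP does not say which rule applies to ABQOL.

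**The case against.** The strongest reply is that this is a typing slip that a competent programmer would see through. The label, the citation and the separately administered TABQOL form all identify the right instrument. That is a fair reading and probably the true one. It lowers the likelihood of harm but leaves an operative derivation that says something else.

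The second reply is that little depends on it. This also stands. A reader might infer that the objective of reducing corticosteroid adverse effects is left without a valid measure. The documents do not support that. The objective is served mainly by the Glucocorticoid Toxicity Index at Week 37, an other secondary endpoint with detailed derivations (SAP 6.1.10) and an analysis of covariance (SAP 8.3), and by the summary of corticosteroid-related adverse events (SAP 9.1.1).

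A reader might also infer that TABQOL would duplicate ABQOL exactly, in every patient at every visit, so that disease burden is analysed twice. That cannot be shown. Identity would need the same items, coding and missing-item rule for both totals, and the SAP writes no rule for the ABQOL total. What follows from the text is narrower: read literally, the TABQOL score would be built from ABQOL responses.

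Finally, the missing ABQOL rule might be supplied by the form itself (Protocol Appendix 3), which is not visible here. That is why it is raised as a clarification, not as an error.

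**Conclusion.** The point holds as an internal contradiction of minor severity. The item source in SAP 6.1.8 conflicts with the bullet's own label, with its cited validation study and with the protocol's separation of the two instruments.

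The size is limited to the exploratory TABQOL summaries at six timepoints (Weeks 5, 13, 25, 37, 61 and 109), and only if the line is programmed literally. It would be wrong to conclude that TABQOL will never be computed, because the intended instrument can be identified from the bullet. No primary, key secondary or multiplicity-controlled result is affected.

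The conclusion assumes that no SAP text outside the visible pages gives another TABQOL derivation. It does not depend on which instrument has 17 items.

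**What to change.** In SAP 6.1.8, redefine TABQOL as the sum of the items of the TABQOL questionnaire (Protocol Appendix 4). Before finalising the line, check four things against that form: the count of 17, the 0 to 3 coding of the response options, the direction of scoring, and the rule that one missing item makes the total missing.

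As a secondary clarification, state or cite the ABQOL total-score and missing-item rule, and say that it governs both the change-from-baseline and the score-of-zero endpoints. The rule should come from the instrument's own scoring. No visible passage establishes that the ABQOL total is a plain item sum, so it should not be assumed.

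The cost is one corrected line and one added line or reference in the SAP. Both questionnaires are already collected, and nothing changes in trial conduct, sample size or alpha. The edit belongs before database lock and unblinding, so that no scoring rule is settled with results in view.
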